## **9.2. Derived and Transformed Data**

The following sections provide a general description of the derived and transformed variables used to describe and analyze the data. Separate analysis dataset specifications provide full details on all data derivations and transformations including descriptions of core standard algorithms and standard Oncology algorithms. The analysis dataset specifications will clearly communicate the content and source of the datasets supporting the statistical analyses.

### **9.2.1. Reference Dates**

There are three reference dates:

- The reference date for age is the date of screening.
- The safety reference date is the treatment start date for subjects randomized to the Ofatumumab arm, and will be used to calculate study day for safety measures. Because subjects in the observation arm do not receive treatment, the randomization date will be used as the safety reference date for subjects in this arm.
- The efficacy reference date is the date of randomization and will be used to calculate study day for efficacy measures and baseline characteristics (such as time since initial diagnosis), as well as efficacy durations.

### **9.2.2. Study Day for Safety Measures**

If the date of interest occurs on or after the safety reference date then the safety study day will be calculated as  $(\text{date of interest} - \text{safety reference date}) + 1$ . If the date of interest occurs before the safety reference date then the safety study day will be calculated as  $(\text{date of interest} - \text{safety reference date})$ . There is no safety study day 0.

### **9.2.3. Study Day for Efficacy**

If the date of interest occurs on or after the efficacy reference date then efficacy study day will be calculated as  $(\text{date of interest} - \text{efficacy reference date}) + 1$ . If the date of interest

occurs prior to the efficacy reference date then efficacy study day will be calculated as (date of interest – efficacy reference date). There is no efficacy study day 0.

#### 9.2.4. Duration and Elapsed Time

Durations (e.g., the duration of an adverse event, duration of exposure, etc.) are calculated as the stop date minus the start date plus one.

For elapsed time (e.g., the time since initial diagnosis):

- If the reference date is on or after the event date, then the elapsed time is the reference date minus the event date + 1.
- If the reference date is before the event date then the elapsed time is the reference date minus the event date.

When reporting time to event (TTE) durations [PFS, time to next treatment, overall survival] in months, divide the number of days by 30.4375; to report in weeks divide the number of days by 7; to report in years divide the number of days by 365.25. These algorithms for time to event return decimal numbers, and ignore the actual numbers of days in the months or years between start date and stop date. The "year" used in these algorithms is 365.25 days long, and the "month" is one twelfth of that year.

For converting all other durations (e.g., duration of adverse events, duration of exposure, age) to weeks, months or years use the following:

- To report the duration in weeks divide the number of days by 7.
- To report the duration in months use:  
 $(\text{YEAR}(\text{stopdate} + 1) - \text{YEAR}(\text{startdate})) * 12 + (\text{MONTH}(\text{stopdate} + 1) - \text{month}(\text{startdate}) - 1) + (\text{DAY}(\text{stopdate} + 1) > = \text{DAY}(\text{startdate}))$
- To report the duration in years use:  
 $\text{intck}(\text{'year'}, \text{startdate}, \text{stopdate} + 1) - (\text{month}(\text{stopdate} + 1) < \text{month}(\text{startdate}) \text{ or } (\text{month}(\text{stopdate} + 1) = \text{month}(\text{startdate}) \text{ and } \text{day}(\text{stopdate} + 1) < \text{day}(\text{startdate})))$

The algorithms above for age and duration return whole numbers for months and years, accurately accounting for the actual numbers of days in the months or years between the start date and the stop date.

#### 9.2.5. Imputation of Partial Dates

Imputed partial dates will not be used to derive study day, duration (e.g., duration of adverse events), or elapsed time variables. In addition, imputed dates are not used for deriving the last contact date in overall survival analysis dataset.

With the exception of new anti-cancer start date on the Oncology time to event analysis dataset and exposure end date on the Exposure analysis dataset, imputed dates will also not be stored on datasets.

Imputed dates will not be displayed in listings. However, where necessary, display macros may impute dates as temporary variables for the purpose of sorting data in listings only. In addition partial dates may be imputed for ‘slotting’ data to study time periods (see Section 9.3) or for specific analysis purposes as outlined below.

The partial date imputation will follow ADaM conventions. The ADaM approach is to populate the numeric date variables with the imputed date and add a flag variable to the dataset that indicates the level of imputation.

The flag variable can contain the values: blank, 'D', 'M', 'Y'.

blank: indicates that no imputation was done

D='Day': indicates that the day portion of the date is imputed

M='Month': indicates that the month and day portions of the date are imputed

Y='Year': indicates that the entire date (year, month, and day) is imputed

Example of Date Variables:

XYZD\_ - character date variable

XYZDT - numeric date variable

XYZDTFL - flag variable

Details on imputing partial dates for specific datasets are outlined below.

**Adverse Events (AE):**

Imputations in the adverse events dataset are used for slotting events to the appropriate study time periods and for sorting in data listings.

Dataset	Date	Missing Element	Rule
Adverse Events (AE)	Start Date	day, month, and year	
 
• No Imputation for completely missing dates
 

		day, month	
 
• If study treatment start date is missing (i.e. subject did not start study treatment), then set start date = January 1.
 
• Else if study treatment start date is not missing:                             
 
○ If year of start date = year of study treatment start date then                                     
 
• If stop date contains a full date and stop date is earlier than study treatment start date then set start date = January 1.
 
• Else set start date = study treatment start date.
 
 
 
○ Else set start date = January 1.
 
 
 

Dataset	Date	Missing Element	Rule
		day	
 
• If study treatment start date is missing (i.e. subject did not start study treatment), then set start date = 1st of month.
 
• Else if study treatment start date is not missing: 
 
○ If month and year of start date = month and year of study treatment start date then 
 
• If stop date contains a full date and stop date is earlier than study treatment start date then set start date= 1st of month.
 
• Else set start date = study treatment start date.
 
 
 
○ Else set start date = 1st of month.
 
 
 

	End Date		
 
• No imputation for partial end dates will be performed
 

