### 9.3. Study Time Periods

Adverse events, concomitant medications, blood product, death, subject disposition, ECOG, laboratory, image data, vital signs, constitutional symptoms, lymph node examination, organ examination, biomarker, and questionnaire data (EORTC QLQ-C30, EORTC QLQ-CLL16, and EQ-5D) will be assigned to the treatment periods defined below. Flag variables indicating the treatment period will be added to these datasets.

**Pre-therapy** is defined as the time prior to the subject's first dose of study treatment for subjects randomized to the ofatumumab arm. For subjects randomized to the "No further treatment (observation)" arm, pre-therapy is defined as the time prior to the subject's randomization date.

**On-treatment** is defined as the time from start date/time of study treatment until the end date/time of the study treatment + 30 days for subjects randomized to the ofatumumab arm. The start date of the on-treatment phase is the date of the first dose of study drug. The end of study treatment is defined as the last dose of planned treatment. For subjects randomized to the "No further treatment (observation)" arm, on-treatment is defined as the time from randomization until the date of entry into follow-up.

There are specific rules to handle the cases where start date/time is equal to start date/time of study treatment or the start date/time is missing for different classes of data sets:

- For interventions and events, including adverse event, concomitant medications, blood product, death, and disposition, i.e., if the date/time is equal to start date/time of study treatment or time is not available and the date is equal to start date of study treatment, the flag will be set to on-treatment. If the start date is missing, and the end date/time is before start date/time of study treatment, the flag will be set to pretreatment. If start date is missing and end date/time is not before the start date/time of study treatment, or both start date and end date are missing, the flag will be set to on-treatment.

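### Partial AE onset dates are imputed against a treatment start date that the observation arm does not have, so some early observation AEs are flagged as pre-therapy

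*SAP*

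**What the plan says.** The AE part of SAP 9.2.5 gives the purpose of the rule: "Imputations in the adverse events dataset are used for slotting events to the appropriate study time periods and for sorting in data listings". Its only anchor is the study treatment start date.

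- **No treatment start date.** Year-only onset: "If study treatment start date is missing (i.e. subject did not start study treatment), then set start date = January 1". Day-missing onset: "If study treatment start date is missing (i.e. subject did not start study treatment), then set start date = 1st of month". Neither line checks the result against randomization or against the stop date.
- **Treatment start date present, day missing.** The test is "If month and year of start date = month and year of study treatment start date then". If it is met, and no full stop date precedes first dose, "Else set start date = study treatment start date". If it is not met, "Else set start date = 1st of month". The year-only rule has the same structure, with a match on year and 1 January as the default.

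Elsewhere the SAP anchors the observation arm to randomization. In 9.2.1, "the randomization date will be used as the safety reference date for subjects in this arm". Section 9.2.7 does the same for baseline. In 9.3, "Pre-therapy is defined as the time prior to the" first dose on ofatumumab and, on observation, as the time before randomization; the observation on-treatment period then runs from randomization to entry into follow-up.

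**The concern.** The branch for a subject who never started treatment suits an ofatumumab subject who was randomized but not dosed. Read literally, it also takes in every observation subject. The period flag of an early AE with an incomplete date then depends on the arm and not on the event. SAP 12.2 collects observation AEs from Visit 1, so placing a collected AE before randomization generally also conflicts with the collection rule.

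At stake is any safety summary that uses a start bound. There the rule can remove events from observation but not from ofatumumab, which would make the ofatumumab arm look worse by comparison.

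**Working it through.** **1. The rule on worked dates.** Take 15 June 2012 as the anchor in both arms (first dose on ofatumumab, randomization on observation), with no stop date before it.

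| Recorded onset | Ofatumumab | Observation, as written | Observation, anchored to randomization |
|---|---|---|---|
| June 2012 | 15 Jun 2012 | 1 Jun 2012 (pre-therapy) | 15 Jun 2012 |
| September 2012 | 1 Sep 2012 | 1 Sep 2012 | 1 Sep 2012 |
| 2012 | 15 Jun 2012 | 1 Jan 2012 (pre-therapy) | 15 Jun 2012 |
| 2013 | 1 Jan 2013 | 1 Jan 2013 | 1 Jan 2013 |

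The arms differ only when the recorded month (or year, for a year-only date) is that of the anchor. A subject randomized on the 1st of the month (or on 1 January) escapes.

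**2. Share of partial dates affected.** The documents give no figure to reproduce. Assume that onsets are uniform over an AE window of W days, that randomization dates are uniform over the calendar, and that first dose is on the day of randomization. The longest observation window follows from Visit 14 at Week 97 (protocol Appendix 1) plus 60 days: (97 − 1) × 7 + 1 + 60 = 733 days. Windows of 365 and 183 days stand for subjects who leave observation early. With L the length of a month (30.4375 days) or year (365.25 days), the share of onsets in the anchor's own month or year is L/(2W) if W ≥ L, and 1 − W/(2L) otherwise.

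| W (days) | Day missing: formula | Simulated | Day and month missing: formula | Simulated |
|---|---|---|---|---|
| 733 | 30.4375/1466 = 2.1% | 2.0% | 365.25/1466 = 25% | 25% |
| 365 | 30.4375/730 = 4.2% | 4.1% | 1 − 365/730.5 = 50% | 50% |
| 183 | 30.4375/366 = 8.3% | 8.0% | 1 − 183/730.5 = 75% | 75% |

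The simulation (200,000 draws per cell) runs slightly lower for day-missing dates because subjects randomized on the 1st are not moved. On ofatumumab the share is 0% in every cell. With observation anchored to randomization it is 0% in both arms.

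**3. What that could mean in events.** A middle case takes exponential PFS with the observation median of 16.89 months reported in the final-analysis SAP, and an AE window to the earlier of progression and 24 months, plus 60 days (mean 17.3 months). The shares are then 0.029 (day missing) and 0.318 (year only). The rates of partial dates must be assumed: 10% to 20% of onsets lacking the day, 2% to 5% lacking day and month.

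- Low: 0.10 × 0.029 + 0.02 × 0.318 = 0.009
- High: 0.20 × 0.029 + 0.05 × 0.318 = 0.022

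About 70% of each total comes from the assumed year-only rate. Without it the figures are 0.10 × 0.029 = 0.3% and 0.20 × 0.029 = 0.6% of observation events. These are events flagged pre-therapy, not events shown to be missing from a table.

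**4. Where the flag can matter.** SAP 12 includes all collected events unless otherwise specified. Two places do specify. SAP 12.2 lists tables running from the start of treatment to 60 days after last dosing, among them infections, decreased counts, autoimmune haematological complications, cardiac events and secondary malignancies. The infection summaries of SAP 12.3 use the treatment and follow-up periods pooled. Neither states a start bound for observation. If the bound is randomization, as 9.2.1 and 9.3 imply, the affected observation events fall outside it.

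**5. Partial against missing dates.** Under 9.3 an AE with neither start nor end date is flagged on-treatment. A partly known date can therefore be treated less favourably than an unknown one.

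**The case against.** A reader might infer that observation AEs with partial dates in general drop out of the AE comparison, and that the ofatumumab excess is therefore inflated. The documents do not support this.

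- The default in SAP 12 keeps all collected events, and no section removes AEs flagged pre-therapy.
- The 9.3 flag is not shown to select the AE tables. The ofatumumab on-treatment period ends 30 days after the last dose, whereas the tables use 60 days. The titles of the planned 60-day outputs carry only an upper bound.
- Partial dates in a later month (or later year, if year-only) are imputed identically. In the calculation above, 92% to 98% of day-missing onsets get the same date in both arms.
- The tables count subjects once per term at maximum grade, so one re-slotted event need not change a count.
- SAP 9.2 leaves full derivations to separate dataset specifications, which are not among the documents and might set an anchor for observation.

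All of this stands, and it confines the point to period-bounded summaries. It does not rescue the rule as written. Nothing visible supplies an anchor, and the same construction recurs for concomitant medications and blood products, which suggests that these conventions were not adapted to an untreated arm. The later SAPs also carry the earlier data rules and conventions forward.

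**Conclusion.** The point holds in a narrow form. The SAP gives an arm-dependent and wrong period flag to observation AEs whose partial onset lies in the month of randomization (day missing) or the year of randomization (day and month missing), and it contradicts its own safety reference date. The main AE summaries are not affected. Period-bounded summaries could lose events from observation only, so the direction of any error is known.

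The size is unknown because the number of partial dates is not reported, and it is probably small. The 0.9% to 2.2% rests on assumed rates of partial dates, uniform onsets and an exponential PFS curve, and would apply only to tables that use the start bound. The correction is worth making because it is cheap and uses a definition that the SAP already contains.

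**What to change.** 1. In the AE table of SAP 9.2.5, replace the study treatment start date by the safety reference date of 9.2.1: first dose for ofatumumab, randomization for observation. Keep the test on a full stop date. The missing-anchor branch then applies only to subjects randomized to ofatumumab and never dosed.
2. Use the same anchor in the 9.3 rules for events whose date equals the anchor or is missing.
3. In the 60-day tables of 12.2, state randomization as the start bound for observation.
4. For concomitant medications and blood products, re-anchor both the partial-date table in 9.2.5 and the rule in 9.3.1. Changing the first alone does nothing, because 9.3.1 classes start and end as BEFORE for anyone who has taken no study treatment, whatever date is imputed.

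The cost is a few lines of SAP text and the matching change in the derivation programs. No new data are needed. A count by arm of partial AE onset dates in the month or year of the anchor would show whether any table changes.

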### Anti-Cancer Therapy and Radiotherapy:

Start and end dates are generally not imputed. If start or end dates need to be imputed for an analysis (e.g., to calculate duration or elapsed time as covariates for efficacy analyses), the rules for imputation will be defined within the algorithm of the derived covariate. Additionally, post treatment anti-cancer therapy and radiotherapy start dates may be imputed to determine date of new anti-cancer therapy. In this case only, the date of new anti-cancer therapy (not all anti-cancer therapy and radiotherapy start dates) will be stored on appropriate efficacy datasets. Imputed partial dates will not be used to derive time since most recent prior therapy. In addition, the cancer therapy treatment status variable, and not any variables that use imputed partial dates, will be used to differentiate prior and follow-up anti-cancer therapy and radiotherapy.

Dataset	Date	Missing Element	Rule
Anti-Cancer Therapy Radiotherapy	Start Date	day, month, and year	
 
• No Imputation for completely missing dates
 

		day, month	
 
• If partial date contains a year only set to January 1st.
 

		day	
 
• If partial date contains a month and year set to the 1st of the month.
 

	End Date		
 
• No imputation for partial end dates will be performed
 

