**Time to Event:**

Start dates for follow-up anti-cancer therapy, radiotherapy (where applicable), and surgical procedures (where applicable) will be temporarily imputed in order to define event and censoring rules for progression-free survival, response rate, or duration of response (i.e. start date for new anti-cancer therapy). Dates will only be imputed when a month and year are available but the day is missing. The imputed date(s) will not be stored on the anti-cancer therapy, radiotherapy, or surgical procedure datasets. The following rules will be used to impute the date when partial start dates are present on anti-cancer therapy radiotherapy, and/or surgical procedures dataset[s]:

Dataset	Date	Missing Element	Rule
Anti-Cancer Therapy  Where applicable:  Radiotherapy  Surgical Procedures	Start Date	day, month, and year	
 
No Imputation for completely missing dates
 

		day, month	
 
No imputation for missing day and month (note the eCRF should only allow for missing day)
 

		day	
 
If partial date falls in the same month as the last dose of study treatment, then assign to earlier of (date of last dose of study treatment+1, last day of month).
 
If partial date falls in the same month as the subject's last assessment and the subject's last assessment is PD, then assign to earlier of (date of PD+1, last day of month).
 
If both rules above apply, then assign to latest of the 2 dates
 
Otherwise, impute missing day to the first of the month.
 

	End Date		
 
No imputation for partial end dates will be performed
 

The date of new anti-cancer therapy is derived as the earliest date of new anti-cancer therapy (e.g., chemotherapy), radiotherapy (where applicable), or cancer related surgical procedure (where applicable) and will include imputed dates. If the date of new anti-cancer therapy is an imputed date, then the date of new anti-cancer therapy flag variable is assigned the value of 'D' to indicate that the day portion of the date is imputed (following ADaM convention).

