- If anti-cancer therapy is started without documented disease progression or is started prior to documented disease progression, then PFS will be censored at the date of the last adequate assessment that is no later than the date of initiation of anti-cancer therapy (i.e. if an assessment occurs on the same day as the start of new anti-cancer therapy the assessment will be used as it will be assumed the assessment occurred prior to the administration of new anti-cancer therapy). The date of response at the last adequate assessment will be used as the censoring value.

- If a subject has only a baseline visit or does not have an adequate assessment that is not later than the date of initiation of anti-cancer therapy, PFS will be censored at the date of randomization.

If a subject has not progressed, has not died or has not started new-anti-cancer therapy, then PFS will be censored at the date of the last adequate assessment defined as an assessment where the investigator determined response and components of lab and clinical parameters (blood, lymph nodes, organ and constitutional symptoms) are available. The date of response will be used as the censoring date.

The assignments for progression and censoring dates for PFS are specified in the following table

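### SAP 9.2.5 gives two conflicting rules for dating new anti-cancer therapy when the day is missing; the one meant for PFS has a last-dose clause that only the ofatumumab arm can use, and time to next therapy is assigned neither

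*SAP*

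**What the plan says.** SAP 9.2.5 (Imputation of Partial Dates) handles the start of later therapy in more than one place.

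- **Anti-Cancer Therapy and Radiotherapy.** Dates are generally left alone, but "post treatment anti-cancer therapy and radiotherapy start dates may be imputed to determine date of new anti-cancer therapy", and the result is kept on the efficacy datasets. If only the day is missing: "If partial date contains a month and year set to the 1st of the month". If day and month are missing, the date becomes 1 January. The Surgery table has the same two rules.
- **Time to Event.** Start dates of follow-up therapy are "temporarily imputed in order to define event and censoring rules for progression-free survival", response rate and duration of response. "If partial date falls in the same month as the last dose of study treatment", the date is the earlier of last dose plus one day and month end. If the last assessment is PD and falls in that month, "assign to earlier of (date of PD+1, last day of month"). If both clauses apply, the later date is taken. "Otherwise, impute missing day to the first of the month". A date missing both day and month is not imputed, with a note that the eCRF should permit only a missing day.
- **Opening text of 9.2.5.** "Imputed partial dates will not be used to derive study day, duration (e.g., duration of adverse events), or elapsed time variables".

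SAP 11.1 then uses the date: "If anti-cancer therapy is started without documented disease progression or is started prior to documented disease progression, then PFS will be censored". The censoring point is the most recent adequate visit not after the start of therapy. For partial dates SAP 11.1 refers only to Section 9, and its wording implies that dates missing both day and month will be imputed. SAP 11.2 defines time to next therapy from randomisation to the next CLL treatment and names no imputation rule. SAP 9.2.1 confirms that observation subjects receive no treatment.

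**The concern.** The start of next therapy decides between event and censoring in the primary endpoint, and it is itself the event in the first endpoint of the sequential secondary testing order (SAP 7 and 8.4). A date with this role needs one rule that behaves the same way in both arms. Here the plan has two rules for one derived variable. A clause in the more specific rule is tied to dosing, which exists in one arm of an open-label trial. The endpoint that depends on the date most directly is assigned to neither rule. At stake are arm-dependent censoring dates in PFS, and an event time for time to next therapy that is left to the programmer.

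**Working it through.** **Inputs.** Date rules: SAP 9.2.5. Censoring rules, including PD counting first when PD and therapy share a date: SAP 11.1 and its Table 1. Assessment interval of 8 weeks (56 days): SAP 9.2.12. Target of 280 PFS events: SAP 5.1. The PD-to-therapy lag, the share of starts with no day and the share of subjects treated early are assumptions; the documents give none of them.

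**Plan figure used as denominator.** With HR = 28/39.2 = 0.714, Schoenfeld's formula gives 4 × (1.960 + 0.842)² / (ln 0.714)² = 31.40 / 0.1132 = 277.3, so 278 events. The stated 280 is consistent and is not in dispute.

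**Worked dates.** The current visit is 15 March, the previous one 18 January (56 days earlier), and therapy is recorded as March with no day.

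| Case | Rule | Therapy dated | PFS |
|---|---|---|---|
| A. PD on 15 March, last assessment | Time to Event, either arm | 16 March | event 15 March |
| A. Same | 1st-of-month table | 1 March | censored 18 January |
| B. No PD, ofatumumab dosed 15 March | Time to Event | 16 March | censored 15 March |
| B. No PD, observation | Time to Event | 1 March | censored 18 January |
| C. PD on 15 March, later assessment in April, dosed at PD visit | Time to Event | 16 March | event 15 March |
| C. Same, observation or last dosed 18 January | Time to Event | 1 March | censored 18 January |

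Case A shows that the tables disagree. Case B shows the arm difference inside the rule written for PFS. Case C shows the narrow route to a change in event status under that rule: PD is not the last assessment, so the PD clause lapses, and only a dose around the PD visit rescues the event.

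**How often case B bites when the day is missing.** The arms differ when therapy starts in the same calendar month as the visit and the visit is not on the 1st. Over all 365 visit dates of a year, the share that differ is 93% at an assumed 1-day lag, 74% at 7 days, 51% at 14 days, 28% at 21 days and 5% at 28 days. Each affected pair differs by 56 days.

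**Size of case A if the 1st-of-month table were applied to PFS.** The same shares apply (51% at 14 days, 0% at 42 days). Under the Time to Event rule with PD as last assessment, the share is 0% at every lag. Events lost = 280 × (share treated about 14 days after PD) × (share with no day) × 0.507:

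- low: 280 × 0.10 × 0.02 × 0.507 = 0.3
- high: 280 × 0.50 × 0.20 × 0.507 = 14.2

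At the high end, Schoenfeld power would go from 0.804 at 280 events to 0.783 at 265.8, if later events did not replace those lost. This conditional figure does not describe what the plan prescribes.

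**Day and month both missing.** The Anti-Cancer Therapy table gives 1 January, the Time to Event table gives no date, and SAP 11.1 implies imputation. A 1 January date would precede the 15 March PD and censor it.

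**Time to next therapy.** SAP 9.2.4 lists it with the time-to-event durations, 9.2.5 bars imputed dates from durations, and the Time to Event table does not name it. Read literally, a subject with a known month of therapy has an event and no date. If imputation is allowed, any day chosen in the right month is wrong by at most 30 days, or 30 / 30.4375 = 0.99 month on the SAP 9.2.4 scale.

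**The case against.** A reader might infer from the 1st-of-month table that the plan places therapy before the progression that prompted it and so censors PD events. The documents do not support that. The Time to Event rule is the specific one: it names PFS and its PD clause works identically in both arms. It also flags an imputed therapy date only as day-imputed, which fits a rule that never imputes the month. After progression, subjects are followed mainly for survival (Protocol 3.1.4), so PD will usually be the last assessment. The flip in case A therefore needs a programmer to follow the wrong table. That risk comes from the loose pointer in SAP 11.1.

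A reader might also infer that time to next therapy is unanalysable for every subject with a missing day. That goes too far. SAP 11.2 says it is analysed as PFS is, and 9.2.5 lets the imputed therapy date be stored on the time-to-event dataset. The plan is unclear here, but the endpoint can still be computed.

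Other parts of the defence also stand. The case with day and month missing should not arise if the eCRF works as noted. The arm difference needs no documented PD, a dose in the month therapy starts, and a missing day; ofatumumab subjects last dosed in an earlier month get the same fallback as observation. For PFS, planned Tables 2.3000 (all events included) and 2.3050 (new therapy counted as an event) in the SAP for the 280-event analysis test sensitivity to this censoring. Full derivations sit in dataset specifications that are not available here.

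None of this removes the one-arm clause or gives time to next therapy a stated rule.

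**Conclusion.** The point holds as a drafting conflict with one real asymmetry. It should be corrected but does not threaten the result. Three things survive:

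1. Two tables date the same variable differently, and SAP 11.1 does not choose between them.
2. The last-dose clause can operate in one arm only, which moves the censoring of otherwise identical subjects by about 56 days and changes event status only in the unusual setting of case C.
3. Time to next therapy is not assigned a rule.

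The number of affected dates cannot be derived from the documents; the shares and counts above rest on assumed lags and missing-day rates. The reported interim result (HR 0.50, 95% CI 0.38 to 0.66, p<0.0001) leaves little room for this to alter the PFS conclusion, and the later analyses are declared descriptive. The interim data rules are carried into the 280-event analysis, and the final analysis keeps the earlier conventions. Time to next therapy (Table 2.1130) is produced in both, so the ambiguity persists there.

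**What to change.** In SAP 9.2.5:

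- Make the Time to Event table the only rule for therapy after randomisation. Limit the 1st-of-month and 1 January rules in the Anti-Cancer Therapy and Surgery tables to prior therapy, or cross-refer them to it.
- Replace the last-dose anchor with one that both arms have, such as the last adequate assessment in that month plus one day, capped at month end. Case B is then censored on 15 March in both arms. Substituting a visit date in the observation arm alone would not do: an ofatumumab subject who has stopped dosing but still attends visits would then fall back to the 1st while the observation subject would not.
- Key the PD clause to any documented PD in that month, so that case C is an event in both arms. This assumes PD came before therapy within the month, a convention that should be stated.
- State that time to next therapy uses the same date, with an explicit exception to the bar on imputed dates in durations.

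In SAP 11.1, name the Time to Event table and delete the reference to dates missing both day and month.

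The cost is a few lines of text and one derivation, with no new data. The clinical study report should state which rule was used for analyses already run and how many therapy dates in each arm lacked a day.
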